9.16.3 HANDLING OF ADVERSE EVENTS

All adverse events resulting in discontinuation from the study should be followed until resolution or stabilization. Patients should be followed for AEs for 30 calendar days after discontinuation or completion of protocol-specific. All new AEs occurring during this period must be reported and followed until resolution unless, in the opinion of the investigator, these values are not likely to improve because of the underlying disease. In this case, the investigators must record his or her reasoning for this decision in the patient's medical record and as a comment on the eCRF. After 30 days, only AEs, SAEs, or deaths assessed by the investigator as treatment related are to be reported.

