1.4 RATIONALE FOR PHASE 2 STUDY

Based on the success of Phase I trials of PI3K inhibitor idelalisib in patients with iNHL Gopal et al performed a Phase 2 randomized clinical trial involving 123 patients with relapsed and refractory iNHL with prior rituximab and alkylator based therapy. After a median follow-up of 9.7 months, the median time to a response was 1.9 months, the median duration of response was 12.5 months, and the median progression-free survival was 11 months. The response rate was 57% (71 of 125 patients), with 6% meeting the criteria for a complete response. However up to 54 % of patients in the clinical trial experienced a grade 3 or higher adverse event, with discontinuation of idelalisib in 20 % of the patients. Some of the most frequently reported adverse events of grade 3 or higher were diarrhea (in 13% of the patients), pneumonia (in 7%), and dyspnea (in 3%)⁸. Combining idelalisib with other agents resulted in greater episodes of grade 3 or higher events including death. In addition to autoimmune toxicity multiple episodes of severe sepsis were reported with increasing opportunistic infections suggesting possible immune deficiency.¹¹⁻¹³ A recent safety analysis of 3 Phase III studies in subjects with previously untreated CLL (bendamustine /rituximab ± idelalisib) and previously treated indolent B-cell NHL (rituximab ± idelalisib and bendamustine/rituximab ± idelalisib) were recently halted because of an excess of deaths and serious adverse events among patients treated in the idelalisib-containing groups (combined mortality rate, 49/664 [7.4%] vs 14/402 [3.5%])

TGR-1202 (umbralisib) is a PI3K inhibitor with an improved safety profile. In an integrated analysis of two Phase I studies, 165 patients with non-Hodgkin's lymphoma, including CLL, were treated with TGR-1202. Adverse events such as nausea, diarrhea, fatigue, headache, vomiting and cough were the most commonly reported events, the majority of which were Grade 1 and 2. The only Grade ≥ 3 adverse event in more than 10% of patients was neutropenia (18%). Discontinuation due to an adverse event with TGR-1202 was reported 8% of patients.

The purpose of this study is to evaluate the safety and efficacy of TGR-1202 in previously treated non-follicular indolent non-Hodgkin's lymphoma patients.

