2.2 EFFICACY ENDPOINTS

Progression-free survival (PFS)

PFS is defined as the interval from Cycle 1/Day 1 to the earlier of the first documentation of definitive disease progression or death from any cause. Definitive disease progression based on revised response criteria for malignant lymphoma (Cheson et al, 2014 and Owen et al 2013).

Time to treatment failure (TTF)

TTF is defined as a composite endpoint measuring time from Cycle 1/Day 1 to discontinuation of treatment for any reason, including disease progression, treatment toxicity, and death.

Overall response rate (ORR)

ORR is defined as sum of CR and PR (and VGPR, MR for patients with WM) rates.

Duration of response (DOR)

DOR is defined as the interval from the first documentation of CR or PR or VGPR or MR to the earlier of the first documentation of definitive disease progression or death from any cause.

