9.17.2 SERIOUS ADVERSE EVENT REPORTING BY INVESTIGATORS

It is important to distinguish between “serious” and “severe” adverse events, as the terms are not synonymous. Severity is a measure of intensity; however, an AE of severe intensity need not necessarily be considered serious. For example, nausea which persists for several hours may be considered severe nausea, but may not be considered an SAE. On the other hand, a stroke which results in only a limited degree of disability may be considered only a mild stroke, but would be considered an SAE. Severity and seriousness should be independently assessed when recording AEs and SAEs on the eCRF.

Adverse events classified by the treating investigator as **serious** require expeditious handling and reporting to the Sponsor in order to comply with regulatory requirements. Serious adverse events may occur at any time from the signing of the informed consent form through the 30-day follow-up period after the last study treatment. Sponsor or designee should be notified of all SAEs, regardless of causality, within 24 hours of the first knowledge of the event by the treating physician or research personnel.

To report an SAE, see the appropriate form.

All SAEs (regardless of causality assessment) occurring on study or within 30 days of last study treatment should be immediately reported to the sponsor as SAEs within the CRF and followed until resolution (with autopsy report if applicable).

NHL progression or death due to NHL progression should be reported by the investigator as a serious adverse event only if it is assessed that the study drugs caused or contributed to the NHL progression (i.e. by a means other than lack of effect). Unrelated events of NHL progression should be captured on the appropriate eCRF.

The investigator must review and sign off on the SAE data on the SAE report. The SAE should be reported to the Sponsor (or Sponsor designee).

When an SAE is reported to the sponsor or designee, the same information should be entered on the eCRF within 24 hours (1 business day). Transmission of the SAE report should be confirmed by the site personnel submitting the report.

Follow-up information for SAEs and information on non-serious AEs that become serious should also be reported to the sponsor or designee as soon as it is available; these reports should be submitted using the appropriate SAE form. The detailed SAE reporting process will be provided to the sites in the Safety Monitoring Plan.

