9.20.3 DEATHS

Deaths that occur during the protocol-specified AE reporting period that are attributed by the investigator solely to progression of the patient's NHL for up to 30 days post the last dose of study drug will be recorded on the appropriate study eCRF and reported on the Adverse Event page of the eCRF, i.e. are exempted from expedited reporting. All other on-study deaths, regardless of attribution, will be recorded on an SAE Report Form and expeditiously reported to the Sponsor.

When recording a serious adverse event with an outcome of death, the event or condition that caused or contributed to the fatal outcome should be recorded as the single medical concept on the Adverse Event page of the eCRF. If the cause of death is unknown and cannot be ascertained at the time of reporting, record "Death NOS" on the eCRF Adverse Event page.

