Any secondary malignancy event must be reported via the SAE form (in addition to the routine AE reporting mechanisms). Any malignancy possibly related to cancer treatment should also be reported via the routine reporting mechanisms outlined in the protocol.

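### The attribution limit on reporting after 30 days (9.16.3) contradicts the secondary-malignancy rule (9.20.6) and, depending on the undefined term 'on-study', the death and SAE rules (9.20.3, 9.17.2)

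*Combined protocol and SAP*

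**What the plan says.** Section 9.16.3 sets a 30-day AE period after protocol treatment ends and then restricts what is reported: "After 30 days, only AEs, SAEs, or deaths assessed by the investigator as treatment related are to be reported".

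Three other sections bear on the same events.

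- Section 9.20.6, on events of special interest: "Any secondary malignancy event must be reported via the SAE form (in addition to the routine AE reporting mechanisms". It states no time limit and no causality condition.
- Section 9.20.3 first deals with deaths "attributed by the investigator solely to progression of the patient's NHL for up to 30 days post the last dose of study drug", which go on the eCRF but are exempt from expedited reporting. It continues: "All other on-study deaths, regardless of attribution, will be recorded on an SAE Report Form and expeditiously reported to the Sponsor".
- Section 9.17.2 first gives an SAE window that closes with the 30-day follow-up. It then says: "All SAEs (regardless of causality assessment) occurring on study or within 30 days of last study treatment should be immediately reported to the sponsor".

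Section 2.2 ends both PFS and DOR at the earlier of "first documentation of definitive disease progression or death from any cause". Section 6.5 and the long-term follow-up footnote to the section 5.1 schedule keep patients who stopped without progression under observation, at intervals of about 6 months or by local practice. That runs well past day 30.

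**The concern.** Sites have to follow one reporting rule, and here the sections give different ones for the same event. If 9.16.3 is followed, a late second cancer that 9.20.6 requires is never sent. A late death enters safety reporting only if the investigator attributes it to the drug.

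Attribution is a weak filter in this design. Every patient receives TGR-1202, the investigator knows it, and there is no control group against which to judge a single case. The filter also works in one direction: it can remove a death from the safety count but cannot add one. Patients who stopped for toxicity are among those it reaches.

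The efficacy side needs the same deaths whatever their cause. Two counts of deaths could therefore be reported from one trial, differing by investigator opinion, with no step in the plan to reconcile them. Section 4.1 has the DSMB review efficacy and safety data after database lock, so it would see the same mismatch.

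**Working it through.** The point turns on text, so the check is to run one patient through each rule. Take a patient who stops treatment for toxicity without progression and enters progression follow-up. On day 90 after the last dose there is either a second cancer or a death, and the investigator judges it unrelated.

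| Section | Second cancer, day 90, unrelated | Death, day 90, unrelated |
|---|---|---|
| 9.16.3 | Not reported (it is an AE or SAE) | Not reported (deaths are named) |
| 9.20.6 | SAE form | No rule |
| 9.20.3 | No rule | SAE form if the patient is on study |
| 9.17.2, later sentence | Reported if the patient is on study and it is an SAE | Reported if the patient is on study |
| 2.2 | Not an endpoint event | PFS event, and a DOR event in a responder |

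**Second cancers.** 9.16.3 and 9.20.6 give opposite instructions, and neither refers to the other. No undefined term is involved.

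**Deaths.** The answer depends on whether this patient is on study.

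- Suggesting yes: sections 6.3 and 6.3.1 send a patient whose delay exceeds 28 days off treatment and into progression follow-up. They reserve the end-of-study visit for consent withdrawal or documented progression. Section 9.4 tabulates discontinuation of treatment and of study as separate items.
- Suggesting no: the long-term follow-up footnote in section 5.1 describes these patients as off study. The first SAE window in 9.17.2, the AE period in 9.16.1 and the AE follow-up in 4.4 all close at 30 days.

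The protocol does not settle which applies.

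**Efficacy against safety.** Whichever reading is taken, the death is a PFS event under section 2.2. Under 9.16.3 it is not a reportable safety event. The two counts can differ by the number of such deaths.

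**Size.** The affected deaths are those in patients who stopped without progression, more than 30 days after the last dose, judged unrelated. The documents give none of these shares. A rough illustration needs borrowed figures:

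- Maximum enrolment (synopsis): 20 + 20 = 40.
- Discontinuation for an adverse event (section 1.4, earlier TGR-1202 studies): 8%. Assumed to apply here: 40 × 0.08 = 3.2 patients.
- Crude mortality (section 1.4, idelalisib studies): 14/402 = 3.5% and 49/664 = 7.4%; the stated percentages reproduce. Assumed to apply here: 3.2 × 0.035 = 0.11 and 3.2 × 0.074 = 0.24 deaths.
- If 10 patients stopped without progression, counting physician choice as well: 10 × 0.035 = 0.35 and 10 × 0.074 = 0.74 deaths.

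All four results are below one death, before narrowing to deaths that are both late and called unrelated. The mortality rates come from another drug, with no matching follow-up time. They show only that the number is likely to be small.

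**The case against.** **The sections can be read together.** Section 9.20.6 is a specific rule that adds to routine reporting, and a specific rule can be taken to prevail over a general one. Section 9.20.3 opens with the AE reporting period, so its later sentence on on-study deaths may mean the same 30 days. This is a fair reading for deaths, and it is why that conflict is conditional. For second cancers it depends on a precedence that the protocol does not state, while 9.16.3 says *only*.

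**The analysis sections already cover deaths.** Section 9.15 tabulates deaths and SAEs with no stated attribution limit, and section 9.2 lists all available data. A reader might infer from 9.16.3 that the safety tables would show none of the late unrelated deaths. The documents do not support that: a death recorded for PFS should reach the listings. What remains is that 9.15 does not say which deaths it counts, and nothing reconciles them with the efficacy deaths. The separate SAP and Safety Monitoring Plan, which might settle this, are not among the documents.

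**Class mortality.** A reader might infer that the rule hides the harm for which idelalisib trials were halted. Section 1.4 gives a combined mortality rate for another drug, from studies that mostly added it to other agents, and the excess was seen against control groups. It does not call the figure all-cause, and a single-arm study of at most 40 patients could not show such an excess even with complete reporting.

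**Expected deaths.** A reader might apply those rates to all 40 patients and get 40 × 0.035 = 1.4 to 40 × 0.074 = 3.0 deaths. That counts every death, including those on treatment and from lymphoma, and so does not measure what 9.16.3 filters out.

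**Conclusion.** The concern holds in a limited form. The contradiction between 9.16.3 and 9.20.6 on secondary malignancies is plain from the text. The contradiction with 9.20.3 and 9.17.2 on deaths holds if progression follow-up counts as being on study; otherwise those sections are only ambiguous. On either reading, the safety death count can be lower than the PFS and DOR death count because of an investigator's opinion, and the plan has no reconciliation.

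The number of events affected cannot be derived and is probably small, under one death in the illustration. The case for changing the text is that sites cannot apply it consistently, that the omission runs one way, and that the repair is cheap. The documents do not show that late deaths would vanish from the tables or that a class mortality signal would be hidden.

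**What to change.** 1. Reconcile 9.16.3, 9.17.2, 9.20.3 and 9.20.6, and define 'on-study' once, stating whether it includes progression follow-up. Align the section 5.1 footnote with that definition.
2. In 9.16.3, state that the attribution limit does not override 9.20.6 for secondary malignancies and does not apply to deaths in patients still in progression follow-up.
3. In 9.15, state that the death tabulation covers all deaths known to the study, split at 30 days after the last dose. Give date, cause and attribution for each, and reconcile the list with the deaths used in PFS and DOR.

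This changes reporting and tabulation only, not patient care. It uses follow-up contacts already planned and death dates that PFS already needs. The downside is a few more reports and a possibly higher stated death count.

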9.17 SERIOUS ADVERSE EVENTS

9.17.1 DEFINITIONS OF SERIOUS ADVERSE EVENTS

The definitions of serious adverse events (SAEs) are given below. The investigator is responsible for ensuring that all staff involved in the study are familiar with the content of this section.

An SAE or reaction is defined as any untoward medical occurrence that:

- results in death, is immediately life-threatening,
- requires at least a 24-hour in-patient hospitalization or prolongation of existing hospitalization,
- results in persistent or significant disability/incapacity, and/or
- causes a congenital anomaly/birth defect.

Medical and scientific judgment should be exercised in deciding whether expedited reporting is appropriate in other situations, such as important medical events that may not be immediately life-threatening or result in death or hospitalization, but may jeopardize the patient or may require intervention to prevent one of the other outcomes listed in the previous definition. These should also usually be considered serious. Examples of such events are intensive treatment in an emergency room or at home for allergic bronchospasm; blood dyscrasias or convulsions that do not result in hospitalization; or development of drug dependency or drug abuse.

Progression of malignancy (including fatal outcomes), if documented by use of appropriate method (for example, as per IWG Cheson et al. 2014, should not be reported as a serious adverse event.

A suspected unexpected serious adverse reaction (SUSAR) is defined as an SAE that is suspected to be at least possibly related to study medication(s) and is an unexpected event. SUSAR reporting is encompassed within SAE reporting guidelines as defined in this section.

Treatment within or admission to the following facilities is not considered to meet the criteria of "in-patient hospitalization" (although if any other SAE criteria are met, the event must still be treated as an SAE and immediately reported):

- Emergency Department or Emergency Room
- Outpatient or same-day surgery units

- Observation or short-stay unit
- Rehabilitation facility
- Hospice or skilled nursing facility
- Nursing homes, Custodial care or Respite care facility

Hospitalization during the study for a pre-planned surgical or medical procedure (one which was planned prior to entry in the study), does not require reporting as a serious adverse event to the Sponsor.

9.17.2 SERIOUS ADVERSE EVENT REPORTING BY INVESTIGATORS

It is important to distinguish between “serious” and “severe” adverse events, as the terms are not synonymous. Severity is a measure of intensity; however, an AE of severe intensity need not necessarily be considered serious. For example, nausea which persists for several hours may be considered severe nausea, but may not be considered an SAE. On the other hand, a stroke which results in only a limited degree of disability may be considered only a mild stroke, but would be considered an SAE. Severity and seriousness should be independently assessed when recording AEs and SAEs on the eCRF.

Adverse events classified by the treating investigator as **serious** require expeditious handling and reporting to the Sponsor in order to comply with regulatory requirements. Serious adverse events may occur at any time from the signing of the informed consent form through the 30-day follow-up period after the last study treatment. Sponsor or designee should be notified of all SAEs, regardless of causality, within 24 hours of the first knowledge of the event by the treating physician or research personnel.

To report an SAE, see the appropriate form.

All SAEs (regardless of causality assessment) occurring on study or within 30 days of last study treatment should be immediately reported to the sponsor as SAEs within the CRF and followed until resolution (with autopsy report if applicable).

NHL progression or death due to NHL progression should be reported by the investigator as a serious adverse event only if it is assessed that the study drugs caused or contributed to the NHL progression (i.e. by a means other than lack of effect). Unrelated events of NHL progression should be captured on the appropriate eCRF.

The investigator must review and sign off on the SAE data on the SAE report. The SAE should be reported to the Sponsor (or Sponsor designee).

When an SAE is reported to the sponsor or designee, the same information should be entered on the eCRF within 24 hours (1 business day). Transmission of the SAE report should be confirmed by the site personnel submitting the report.

Follow-up information for SAEs and information on non-serious AEs that become serious should also be reported to the sponsor or designee as soon as it is available; these reports should be submitted using the appropriate SAE form. The detailed SAE reporting process will be provided to the sites in the Safety Monitoring Plan.

Investigators must report SAEs and follow-up information to their responsible Institutional Review Board (IRBs)/Independent Ethics Committee according to the policies of the responsible IRB (Research Ethics Committee).

9.18 SPONSOR SAE REPORTING REQUIREMENTS

Sponsor is responsible for reporting relevant SAEs to the competent authority, other applicable regulatory authorities, and participating investigators, in accordance with ICH guidelines, FDA regulations, and/or local regulatory requirements.

Sponsor is responsible for reporting unexpected fatal or life-threatening events associated with the use of the study drugs to the regulatory agencies and competent authorities within 7 calendar days after being notified of the event. The Sponsor will report all related but unexpected SAEs including non-death/non-life-threatening related but unexpected SAEs (SUSAR) associated with the use of the study medications to the regulatory agencies and competent authorities by a written safety report within 15 calendar days of notification. Following the submission to the regulatory agencies and competent authorities, Investigators and trial sites will be notified of the SUSAR. Investigators must report SUSARs and follow-up information to their responsible Institutional Review Board (IRBs)/Independent Ethics Committee according to the policies of the responsible IRB (Research Ethics Committee).

9.19 RECORDING OF ADVERSE EVENTS AND SERIOUS ADVERSE EVENTS

Investigators should use correct medical terminology/concepts when recording AEs or SAEs on the SAE Report Forms and AE eCRF. Avoid colloquialisms and abbreviations.

All AEs, including those that meet SAE reporting criteria, should be recorded on the AE eCRF; AEs that meet the definition of an SAE should additionally be reported.

9.20 DIAGNOSIS VS. SIGNS AND SYMPTOMS

All AEs should be recorded individually in the patient's own words (verbatim) unless, in the opinion of the Principal Investigator or designated physician, the AEs constitute components of a recognized condition, disease, or syndrome. In the latter case, the condition, disease, or syndrome should be named rather than each individual sign or symptom. If a constellation of signs and/or symptoms cannot be medically characterized as a single diagnosis or syndrome at the time of reporting, each individual event should be recorded as an AE or SAE as appropriate on the relevant form(s) (SAE Report Form and/or AE eCRF). If a diagnosis is subsequently established, it should be reported as follow-up information is available. If a diagnosis is determined subsequent to the reporting of the constellation of symptoms, the signs/symptoms should be updated to reflect the diagnosis.

